This study will include a cross-sectional analysis of data from a consecutive sample of caregiver-child dyads with varying levels of exposure to a fruit and vegetable prescription program (FVPP) that provides one \$15 prescription for fresh produce to every child during pediatric office visits. Considering the importance of dietary patterns during childhood on long-term diet and health¹¹⁻¹³ alongside evidence that indicates adolescence is the specific period when food insecurity has the greatest potential to negatively impact the diet,³⁵ data collection and analyses will focus specifically on children and adolescents ages 8-16 years. A total of 700 caregiver-child dyads (one caregiver and one child per household) will be enrolled in the study, with approximately 200 dyads enrolled at clinic 1 (high exposure); 200 dyads enrolled at clinic 2 (moderate exposure), and 300 dyads enrolled at clinic 3 (no previous exposure to the FVPP). A description of the clinics is provided with our explanation of the 'Setting' for this study.

Dyad enrollment will be based on exposure to the FVPP as defined by caregiver-reported and clinic-verified length of time that the participating child has been a patient at one of three partnering clinics. Accordingly, we expect dyads to cluster based on pediatric clinics as follows: clinic 1 (high exposure), clinic 2 (moderate exposure), and clinic 3 (no previous exposure). A sample of approximately 200 pediatric patients newly exposed to the FVPP at clinic 3 will be followed for a period of two years as part of a non-controlled longitudinal intervention trial that will examine changes in dietary patterns, food security, and weight status over time.

Setting

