- Clinic 3 is the largest pediatric clinic in Genesee County, with Flint as its urban center. Expansion of the FVPP to clinic 3 will substantially increase program reach among vulnerable children and families living in Flint. Last year, clinic 3 had over 12,000 pediatric visits. It has a comparable patient population to clinics 1 and 2, serving only children in need who are residents of Genesee County.

Participants and recruitment

A sample of 250 caregiver-child dyads presenting at clinic 1, 250 caregiver-child dyads at clinic 2, and 350 caregiver-child dyads at clinic 3 will be assessed for eligibility, with 700 total dyads enrolled (anticipated 10-15% not meeting eligibility and 10% refusal based on a previous study). To control for confounders, we will adopt a balancing strategy that consists of recruiting in the study children who have approximately the same age, sex, and race across the three clinical settings. These children will not be balanced according to variables pertaining directly to the exposures (e.g., duration of FVPP exposure).

With target samples of 200, 200, and 300 caregiver-child dyads enrolled in clinic 1 - high exposure, clinic 2 - moderate exposure, and clinic 3 - no previous exposure, respectively, we have well above 90% power to jointly detect modest relative differences in the baseline mean intake of vegetables of 20% from clinic 2 to clinic 3 and 38% from clinic 1 to clinic 3. This calculation assumes an underdispersed Poisson model with a dispersion parameter of 0.82, derived using previously published data on the mean intake of vegetables of 0.72 cup and a standard deviation of 0.77 cup in the settings with no prior FVPP exposure.²⁰ Likewise, with 300 caregiver-child dyads enrolled in clinic 3, we have well above 90% power to detect a modest temporal improvement in the mean intake of vegetables of 25% over 12 months (0.72 cup at baseline versus 0.90 cup at 12-month follow-up). This calculation assumes a correlated Poisson model for underdispersed count data with timepoint dispersion parameter of 0.82, and a modest temporal correlation of 0.2. Increasing values of the temporal correlation greatly improves the statistical power. Finally, estimation of FVPP effects will specify two-tailed tests with alpha set at the 0.05 level.

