To compare baseline dietary intake, food security, and weight status between pediatric patients with varying levels of exposure to the FVPP, we will collect study measures at baseline from 700 dyads at each of three partnering clinics. To measure changes in diet, food security, and weight status when never-exposed children are introduced to the FVPP, we will follow approximately 200 dyads from clinic 3, collecting study measures at baseline, 12- and 24-month follow-up. In addition to posters, brochures, and websites that explain the FVPP, caregivers at clinic 3 will be reminded of each follow-up visit through reminder cards and telephone calls.

REDCap provides data security measures designed to prevent unauthorized access, disclosure, alteration, and use of data. Data from the completed evaluation tools will be stored in REDCap project database. Children and caregivers will be assigned identification numbers upon enrollment in the study. All data will be de-identified within the data management system, and de-identified data will be exported for analyses.

Any modifications to the approved protocol will be submitted to Michigan State University IRB for review and approval prior to implementation. Furthermore, although the likelihood of any adverse event in this trial is remote, we have formalized our Data and Safety Monitoring Plan to include a designated Data and Safety Monitor. This Monitor will have the authority to recommend termination of the trial if he makes the determination that unacceptable adverse events have taken place. Should any adverse events occur, these will be immediately reported to Michigan State University IRB for review.

Benefits

Completion of our study aims will provide empirical evidence for the effectiveness of Produce Prescription Programs, which were recently added to the US Farm Bill through the Gus Schumacher Nutrition Incentive Program. Our study will share insights regarding the duration and intensity of exposure necessary to influence changes in food security, dietary patterns, and weight status when fruit and vegetable prescriptions are provided to pediatric patients. Furthermore, our results will be especially important to pediatricians and primary care physicians who recognize the consequences of food insecurity among young patients and are seeking tangible solutions that not only provide food to hungry children but ensure that the food provided is high in nutrients needed to support healthy growth and development.

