Reasonably Foreseeable Risks

There are no known risks to participants.

Primary outcome measures

Child dietary patterns

Because the children's dietary patterns across gradients of exposure to the FVPP are of primary interest, we will administer two non-consecutive 24-hour dietary recalls and one validated food frequency screener. The dietary recall data will cover the 24 hours before enrollment and a second 24-hour interval that occurs just before a post-baseline assessment completed by the RA within seven days after baseline. The Automated Self-Administered 24-Hour (ASA-24) Dietary

Assessment Tool will be used for these assessments. The 24-hour dietary recall is a valid measure for assessing the dietary intake of children ages eight years and older.⁴⁹ The RA also will administer Block Kids Food Screener, a food frequency questionnaire, to allow for the assessment of usual and long-term eating behaviors with relatively little administration burden. Block Kids Food Screener has shown good relative validity for children and adolescents.⁵⁰ Its 41 items assess the frequency and quantity in which foods and beverages were consumed over the previous week.

After data collection, a dietary analysis, using the Block Online Analysis System, will provide nutrient estimates and the number of servings by food group. We will use these data to evaluate the mean daily intake of total fruits and vegetables, total vegetables, total fruits, and whole fruits. The Healthy Eating Index (HEI) will be generated from the dietary data for use as a measure of the diet quality of the children.^{51,52}

Child-reported food security

Children ages 12 years and older will complete the Self-Administered Food Security Survey Module for Youth (SAFSSMY). Although the SAFSSMY was found to have adequate internal validity for children ages 12 years and older, it is not recommended for use with younger children.⁴⁷ The sum of affirmative responses (“a lot” or “sometimes”) to module questions will provide the child’s initial raw score on the perceived food security scale, with food security status assigned based on raw score (0-1=high/marginal food security; 2-5=low food security; 6-9=very low food security). This study’s sample size is sufficient for a confirmatory factor analysis based on Item Response Theory, which will be used to evaluate whether the unit weight assigned to each item can be improved upon.

Household food security

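### Reason for visit and acute illness are neither recorded nor adjusted for, so part of any before-after dietary gain at clinic 3 could be recovery from illness

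*Combined protocol and SAP*

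**What the plan says.** Study Design describes "a consecutive sample of caregiver-child dyads with varying levels of exposure". Participants and recruitment refers to "A sample of 250 caregiver-child dyads presenting at clinic 1", with matching groups at clinics 2 and 3. The entry criteria in that section cover age, language, consent and assent, and length of programme exposure. At clinic 3 the exclusions are an already enrolled sibling or a move between clinics. Reason for visit is not mentioned.

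Child diet at baseline has three components, set out under Primary outcome measures, Child dietary patterns:
- First recall: "The dietary recall data will cover the 24 hours before enrollment".
- Second recall: "a second 24-hour interval that occurs just before a post-baseline assessment completed by the RA within seven days after baseline".
- Block screener: "Its 41 items assess the frequency and quantity in which foods and beverages were consumed over the previous week".

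Follow-up applies to about 200 clinic 3 dyads at 12 and 24 months. Data collection procedures says that "caregivers at clinic 3 will be reminded of each follow-up visit through reminder cards and telephone calls". Study Design calls this part of the study non-controlled.

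The Covariates section and the Statistical analysis plan list physical activity, sleep, caregiver weight and height, sociodemographic variables and food-assistance participation, among others. Visit type and current illness are not among them.

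**The concern.** The first baseline recall is tied to the day before a clinic presentation, and some presentations will be for acute illness. The follow-up assessments are tied to the calendar. If a sick child eats less fruit and vegetables, the before measurement is taken at a moment partly selected for low intake and the after measurement is not.

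In Aim 2 no concurrent group would show the same recovery, so it would be counted as programme effect, in the direction the study expects. Aim 3 has a similar asymmetry, because clinic 3 follow-up values are set against clinic 1 values taken at a presenting visit. Aim 1 uses the same baseline procedure at all three clinics, so it is affected only if the share of sick visits differs between them.

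Regression adjustment, propensity scores, mixed models and imputation cannot correct for a variable that was never collected.

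**Working it through.** **Inputs from the documents** (Participants and recruitment, unless stated): mean vegetable intake 0.72 cup, SD 0.77 cup, dispersion 0.82, temporal correlation 0.2, two-sided alpha 0.05, design improvement 0.72 to 0.90 cup (0.18 cup, 25%), 300 dyads in the power statement. About 200 dyads are followed (Data collection procedures).

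**Inputs that are assumed**: share of enrolment visits for acute illness p = 0.20 to 0.50; relative fall in intake on the sick day r = 0.20 to 0.40. The documents give neither figure.

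**Step 1. The plan's own figures.** The dispersion reproduces: 0.77² / 0.72 = 0.823. For the 12-month change, SE = √[0.82 × (0.72 + 0.90 − 2 × 0.2 × √(0.72 × 0.90)) / n].
- n = 300: SE = 0.0596, 0.18 / 0.0596 = 3.02, power = Φ(3.02 − 1.96) = 85.6%. The plan states a value well above 90%, which this model does not reproduce at correlation 0.2.
- n = 200: SE = 0.0730, ratio 2.47, power = 69%.

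The power statement is a separate matter. The model is used here only as a yardstick.

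**Step 2. Size of the artefact with no programme effect.** Take 0.72 cup as usual intake. The fractional baseline deficit is b = p × r × w, where w = 1 if only the first recall is analysed (or if both recalls are affected) and w = 0.5 if the first is averaged with an unaffected second recall. The apparent gain is 0.72 × b in cups, or 1/(1 − b) − 1 relative to the depressed baseline.

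| Case | b | Cups | Share of 0.18 cup | Apparent rise |
|---|---|---|---|---|
| Low, averaged: 0.20 × 0.20 × 0.5 | 0.02 | 0.014 | 8% | 2.0% |
| High, averaged: 0.50 × 0.40 × 0.5 | 0.10 | 0.072 | 40% | 11.1% |
| Low, first recall alone: 0.20 × 0.20 | 0.04 | 0.029 | 16% | 4.2% |
| High, first recall alone: 0.50 × 0.40 | 0.20 | 0.144 | 80% | 25% |

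The averaged rows fit the plan better, because two recalls are collected.

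**Step 3. If the screener is the analysed measure.** Suppose 2 of its 7 days are affected (a further assumption). Then b = 0.04 × 2/7 = 0.011 to 0.20 × 2/7 = 0.057, which is 0.008 to 0.041 cup, or 5-23% of 0.18 cup.

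**Step 4. Effect on the Aim 2 test.** With n = 200 and the same variance model, the chance of a significant change with no programme effect is 0.055 at b = 0.02 and 0.19 at b = 0.10, against a nominal 0.05.

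**Step 5. Cost of excluding acute-visit baselines.** Removing 20-50% of 200 leaves 160 to 100 dyads. Power for the 25% gain is Φ(0.18/0.0816 − 1.96) = 60% at 160 and Φ(0.18/0.1032 − 1.96) = 41% at 100, against 69% with all 200.

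**The case against.** The strongest reply is that baseline diet is not one sick day. A second recall follows within seven days and the screener covers a week. The plan also appears to draw servings by food group from the Block analysis, without saying how recalls and screener are combined. This stands, and it is why the averaged and screener figures are the relevant ones. It is dilution and not removal: the screener week can overlap the illness, and some children may still be unwell at the second recall.

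Both driving inputs are assumed, as is the premise that intake falls on a sick day. With fewer sick visits the artefact becomes negligible: at p = 0.10, r = 0.20 and an unaffected second recall, it is 0.72 × 0.01 = 0.007 cup. This also stands.

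The net direction is not certain. At clinic 3 the second recall may fall after the first prescription, which could raise measured baseline intake. For weight, recovery would look like a gain, against the expectation of less obesity.

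A reader might go further in three ways that the documents do not support:
- That the follow-ups are dedicated booked study visits with well children. The text mentions only fixed time points and reminders, so lower illness at follow-up is an inference.
- That Aim 1 is biased. The clinics are described as serving comparable populations, and nothing shows a different sick-visit mix.
- That the baseline should be postponed until the child is well but kept ahead of the first prescription. This conflicts with a programme that issues a prescription at each office visit, and with the assurance that joining the study does not affect eligibility for it.

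**Conclusion.** The gap is real: enrolment at presentation, a first recall anchored to the preceding 24 hours, calendar-based follow-up, no control in Aim 2, and no illness or visit-type variable in the plan. Together these mean that recovery from illness could not be separated from a programme effect. Aim 3 shares the problem; Aim 1 does so only under a differential sick-visit mix.

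The documents establish the structure but not the size. Under the stated assumptions with an unaffected second recall, the artefact is 0.014-0.072 cup, or 8-40% of the 0.18-cup target. It is smaller if sick visits are rarer or the screener is analysed, and larger if illness also lowers the second recall. The documents do not support a claim that the expected gain is mostly artefact. A proportionate conclusion is that the plan should collect the one variable that would settle the question from its own data.

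**What to change.** 1. Record the reason for visit and whether the child is currently acutely ill, at every assessment in all three clinics, including the 12- and 24-month follow-ups. Reason for visit can come from the medical chart review already planned for exposure (Table 1).
2. Include acute illness as a covariate in the Aim 1 and Aim 3 models, and as a time-varying covariate in the Aim 2 mixed model.
3. Pre-specify an Aim 2 sensitivity analysis that either excludes acute-visit baselines or uses only the second recall for those children. Note with it that the second recall may follow the first prescription.

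The cost is one or two extra fields and a few lines in the analysis plan. The exclusion analysis loses precision: under the assumed shares, power for the 25% gain is about 41-60%, against 69% with all 200 dyads. It should therefore be read by comparing its estimate with that of the main analysis, not by its significance. Neither the timing of the baseline nor that of the prescription needs to change.

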To monitor prescription redemption, FFM vendors will collect paper prescriptions redeemed for fresh produce and turn them into the FFM management office at the end of each month for payment. Prescriptions will be collected, sorted, stored, and entered into a database for tracking purposes. A similar method will be used to track and record monthly prescription redemption through Flint Fresh, including tracking of virtual prescriptions which were introduced during the COVID-19 pandemic as pediatric telehealth visits increased.

Data collection procedures

Consent/assent procedures and data collection at baseline will be carried out in a private clinic location, such as a patient examination room. A trained research assistant (RA) will follow our study's Institutional Review Board (IRB)-approved protocol for consent, child assent, and data collection (e.g., of dietary data). The RA will provide detailed instructions regarding the study, survey completion, and how to make use of an iPad and its interface with a secure digital platform (Research Electronic Data Capture or REDCap). Researchers will copy the signed consent and assent forms at pediatric offices and provide to families upon enrollment in the study or researchers will email copies of signed e-consent and assent and provide to families upon enrollment in the study. Caregivers and children will be told that their participation is voluntary; that they may stop participating at any time; that they may choose how much information they feel comfortable sharing; that their individual identity will not be shared with anyone; and that in the writing of any results, pseudonyms will be used. Families will be told by researchers as well as pediatricians and office staff that their acceptance or refusal to participate in the research study will not impact their eligibility to receive the fruit and vegetable prescription. Each member of the caregiver-child dyad will separately complete a standardized questionnaire with pre-worded demographic and pilot-tested survey questions that assess dietary patterns, food security, and food access.²⁰ The RA will assist children with survey completion. Child body mass index (BMI) percentile and BMI z-score will be calculated based on measured height and weight, as described in the 'Primary Outcome Measures' section. Key constructs and study measures are listed in Table 1.

Table 1. Key Constructs

Domains	Constructs	Measures	Instruments

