Personal Outcomes	Child self-efficacy	
 • Self-efficacy for fruit consumption • Self-efficacy for vegetable consumption • Proxy efficacy to influence parents to make fruits and vegetables available 	
 • Self-efficacy questionnaire^{42,43}
	Caregiver self-efficacy	
 • Self-efficacy to purchase and consume fruits and vegetables 	
 • Selected questions from Food Attitudes and Behaviors Survey⁴⁴
Environmental Outcomes	Exposure to fruit and vegetable prescriptions	
 • Number of months child has been a patient at fruit and vegetable prescription participating pediatric office • Number of fruit and vegetable prescriptions received 	
 • Medical chart review
	Caregiver dietary patterns	Mean daily servings of: 
 • Total fruits • Total vegetables • Total fruits and vegetables 	
 • National Cancer Institute Fruit & Vegetable Intake “All Day” Screener^{45,46}
	Caregiver fruit and vegetable access	
 • Access to fruits and vegetables • Barriers to access • Social support to access 	
 • Food Attitudes and Behaviors Survey⁴⁴ • Michigan Behavioral Risk Factor Surveillance Survey
	Food security	
 • Perceived food security among youth 	
 • Food Security Survey Module for Youth⁴⁷
		
 • Household food security and hunger 	
 • US Household Food Security Module: Six Item Short Form⁴⁸
Behavioral Outcomes	Child fruit and vegetable consumption	Mean daily servings of: 
 • Total fruits • Total whole fruits • Total vegetables • Total fruits and vegetables 	
 • Two non-consecutive dietary recalls⁴⁹ • Block Kids Food Screener⁵⁰
	Child dietary patterns	
 • Nutrient estimates • Number of servings by food groups • Healthy eating index 	
 • Block Kids Food Screener⁵⁰
Secondary Outcomes	Child weight status	
 • Body mass index (BMI) • BMI percentile, BMI z-score 	
 • Measured weight • Measured height

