Caregivers will complete the US Household Food Security Module: Six Item Short Form (National Center for Health Statistics) to assess household food insecurity and hunger.⁴⁸ The sum of affirmative responses (“often”, “sometimes”, “yes”, “almost every month”, “some months but not every month”) on the module will serve as the household’s raw score. Food security status will be assigned based on the raw score (0-1=high/marginal food security; 2-4=low food security; 5-6=very low food security). We will use this data to calculate household food security and hunger. Here also, after planned analyses based on the raw score, a confirmatory factor analysis approach will be taken in a post-estimation exploratory analysis.

Child weight, height, and BMI status

The trained RA will take two successive measurements of each child’s weight and height within the patient examination room, without shoes or heavy outer garments. Then, the RA will enter the data electronically using the REDCap secure digital platform. Weight will be measured to the closest 0.2 kg on a digital platform scale accurate to 200 kg. Height will be measured to the closest 0.1 cm using a portable stadiometer. Body mass index (BMI), which correlates with more expensive and direct measures of body fat in children (e.g., dual-energy x-ray absorptiometry) will be calculated from child weight and height (weight (kg)/[height (m)]²).⁵³ The derived BMI can be categorized into normed percentiles by sex and age to serve as an indicator of overweight and obesity.⁵⁴

Secondary outcome measures

Self-efficacy

Per our theoretical model, improving self-efficacy for consuming fruits and vegetables is important to change dietary behavior.³⁴ A validated questionnaire will be administered at each time point to assess caregiver self-efficacy to purchase and consume fruits and vegetables as well as child self-efficacy to consume fruits and vegetables and proxy efficacy to influence parents to make fruits and vegetables available.^{42,43}

Caregiver dietary patterns

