An alternative balancing strategy based on propensity scores will be used to mitigate potential differences at baseline among participants in the three study groups. These scores will be used to derive an unbiased estimate of the average treatment effect of FVPP on study endpoints. The generalized propensity score to account for multiple levels of treatment in the spirit of Imbens will be estimated with a multinomial logistic regression.⁶² To estimate the FVPP effects, we will use an elaborated multinomial logistic model that includes the child's level, the caregiver's level covariates, and functions thereof (e.g., interactions).

The choice of analytic methods will be guided by the specific aims, the nature of study endpoints and that of relevant data. Independence models will be used to compare baseline dietary intake, food security, and weight status between pediatric patients with varying levels of exposure to the FVPP. Correlated data models will be used to evaluate (1) changes in diet, food security, and

weight status when never-exposed children are introduced to the FVPP; and (2) compare mean follow-up measures of dietary intake, food security, and weight status in the initial no exposure group to baseline measures in the high exposure group.

Comparison of baseline measures based on FVPP exposure

Multiple linear regression will be used to assess the relationship between mean daily intake of fruits and vegetables and level of exposure to the FVPP. A basic logistic regression model will be used to evaluate the adjusted effect of the child-level exposure to the FVPP on the obesity probability. An ordinal logistic regression model will be used to evaluate the adjusted effects of the child-level exposure to the FVPP on food security (measured as an ordinal outcome). Within this class of models, we will entertain the popular proportional odds model with prior evaluation of the assumption of the proportionality of odds across the ordered levels of food security. These analyses will be adjusted for variables such as food assistance program participation, nutrition education program participation, child race, child age, child gender, caregiver-reported income group, caregiver-reported weight status, caregiver education, and child-reported mean daily intake of fruits and vegetables.

Evaluation of changes when children are introduced to the FVPP

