After baseline data collection, periodic follow-up assessments will be conducted to study changes in diet, food security, and weight status among children newly exposed to the FVPP at clinic 3. Because of the repeated nature of the data generated for this aim, we will consider methods that accommodate the within-child and/or the within-caregiver association. For continuous outcomes (e.g., dietary intake), repeated measures models such as linear mixed models and repeated ANOVA models, will be entertained in view of their robustness to certain types of missing data. These classes of models will be used to assess changes from baseline at key points in the study.^{63,64} For ordinal endpoints such as food security (with ordered levels), a generalized linear mixed effects model with cumulative logits will be entertained. To examine whether there is a significant improvement in child-reported food security from baseline, contrast representing the difference in log-odds between baseline and follow-up will be evaluated. Alternatively, GEE counterparts of these likelihood-based models (that use the sandwich-based correction in lieu of the model-based variance-covariance matrix of the parameter estimates) will also be considered.⁶⁵

Comparison of mean follow-up measures in the initial no exposure group to baseline measures in the high exposure group

At follow-up, measures of dietary intake, food security, and weight status in a group of children newly exposed to the FVPP will be compared to baseline measures of children with high exposure to the FVPP (>24 months). For example, to compare measures of dietary intake (at 12 months and 24 months) in the newly exposed group to those of the highly exposed group, the class of linear mixed models and repeated ANOVA models will be considered. These models will be similar to those of aim 2, with the additional flexibility of group-specific time-point effects. For ordinal outcomes (e.g., food security) and binary outcomes (e.g., obesity), a generalized linear mixed effects model will be used. Alternative models such as GEE models will also be entertained.

Discussion

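### For Aim 1 the plan names only a logistic obesity model for weight status; BMI z-score, which will be calculated anyway, could be added as a pre-specified supporting outcome

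*Combined protocol and SAP*

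**What the plan says.** Aim 1, under Study aims and hypotheses, compares baseline weight status between exposure groups. The expectation in the same section is narrower: lower obesity rates with greater exposure.

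On measurement, Data collection procedures states: "Child body mass index (BMI) percentile and BMI z-score will be calculated based on measured height and weight". The weight-status row of Table 1 lists BMI and "BMI percentile, BMI z-score". The section on child weight, height and BMI adds: "The derived BMI can be categorized into normed percentiles by sex and age to serve as an indicator of overweight and obesity". No obesity cut-off is given.

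On analysis, the Aim 1 section of the SAP assigns a model to each outcome. For diet: "Multiple linear regression will be used to assess the relationship between mean daily intake of fruits and vegetables and level of exposure". For weight: "A basic logistic regression model will be used to evaluate the adjusted effect of the child-level exposure to the FVPP on the obesity probability". Food security gets an ordinal logistic model. One adjustment list follows for all three, and it includes the child's reported fruit and vegetable intake. The SAP text never mentions BMI z-score.

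Two general statements bear on this. The SAP opens by promising several techniques to test robustness, and later says: "The choice of analytic methods will be guided by the specific aims, the nature of study endpoints and that of relevant data". For Aim 2 it says: "For continuous outcomes (e.g., dietary intake), repeated measures models such as linear mixed models and repeated ANOVA models, will be entertained". Of the Aim 3 models it says: "These models will be similar to those of aim 2, with the additional flexibility of group-specific time-point effects".

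**The concern.** Aim 1 is about weight status, and the trial will hold a continuous measure of it for each child. The only Aim 1 weight analysis that the SAP names turns that measure into obese or not obese. A child who moves from well above the cut-off to just above it, or from mid-range to lower, contributes nothing to the comparison.

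The stake is how a null obesity result would be read. The only Aim 1 power figure is for vegetable intake, and nothing is offered for weight. If the obesity comparison is inconclusive, a reader cannot tell whether weight is similar across clinics or the binary test was too blunt. A z-score analysis added after the data are seen would be open to the charge of selective emphasis. Naming it beforehand, with a stated rank, avoids that.

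**Working it through.** **The plan's own figure.** For Aim 1 this is power well above 90% for vegetable intake. A 2-df Wald test on log means (variance 0.82/(n × mean), means 0.72, 0.72 × 1.20 and 0.72 × 1.38, n = 300/200/200) has noncentrality 13.21 and power 91%. That covers diet only; there is no weight figure to reproduce.

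**Inputs from the documents** (Participants and recruitment): 200 dyads in clinic 1, 200 in clinic 2, 300 in clinic 3; two-sided 0.05.

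**Assumptions, because the documents are silent:** normal z-score with SD 1; obesity is its upper tail; clinic 3 prevalence p0 of 10% to 40%; unadjusted comparison.

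**Z-score, clinic 1 against clinic 3, even shift of 0.25 SD.** SE = √(1/200 + 1/300) = 0.0913. Then 0.25/0.0913 = 2.739, and power = Φ(2.739 − 1.960) = 78%. The shift detectable with 80% power is (1.960 + 0.842) × 0.0913 = 0.256 SD.

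**Obesity, same shift, worked at p0 = 20%.**
- Cut-off: 0.842. Clinic 1 prevalence: 1 − Φ(0.842 + 0.25) = 13.7%.
- Pooled prevalence: 17.5%. Null SE: √(0.175 × 0.825) × 0.0913 = 0.0347.
- Alternative SE: √(0.1375 × 0.8625/200 + 0.20 × 0.80/300) = 0.0336.
- Power = Φ((0.0625 − 1.960 × 0.0347)/0.0336) = 44%.

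Information kept by the cut is φ(c)²/[p0(1 − p0)], where φ is the normal density and c the cut-off.

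| Clinic 3 prevalence | Clinic 1 after 0.25 SD shift | Obesity power | Information kept | Clinic 1 prevalence needed for 80% power |
|---|---|---|---|---|
| 10% | 6.3% | 30% | 0.34 | 3.5% |
| 20% | 13.7% | 44% | 0.49 | 10.7% |
| 30% | 21.9% | 51% | 0.58 | 19.0% |
| 40% | 30.7% | 56% | 0.62 | 27.9% |

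The last column is a relative drop of 65% at the top of the table and 30% at the bottom.

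**All three clinics** (2-df test, shifts of 0.25, 0.125 and 0 SD in clinics 1, 2 and 3): 69% for z-score; 25%, 35%, 42% and 46% for obesity down the same prevalences.

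**Where the advantage fails.**
- Even shift of 0.10 SD: z-score 19%, obesity 9% to 13%. Neither is informative.
- Only the upper 75% of children shift by 0.25 SD (20,000 simulated t-tests): z-score 56%, obesity still 30% to 56%.
- Only the upper half shift: the mean moves by 0.125 SD and the variance falls to 0.82. Z-score power is about 29%, against 30% to 56% for obesity.

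Obesity power is unchanged in the last two cases because every cut-off lies above the median, so every child who crosses it is among those who shift.

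**The case against.** The strongest reply is that nothing here is wrong. The hypothesis is about obesity rates, logistic regression answers it, and the SAP's general wording already allows a continuous model. Mean z-score asks a somewhat different question, and its advantage needs a broad shift that no part of the protocol predicts. If the programme mainly affects heavier children, z-score gains little or loses. A second weight test also adds a result that may conflict with the first.

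Most of this stands, and it limits the point to a supporting analysis. What it does not remove is that permission is not specification: for Aim 1 the general wording leaves open whether z-score is modelled and how much weight it carries.

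A reader might infer three stronger things that the documents do not support:
- *That the obesity model is invalid or should be replaced.* It matches the stated expectation, and the partial-shift cases show that z-score is not uniformly better.
- *That z-score is left without a model in every aim.* The Aim 2 section provides linear mixed or repeated ANOVA models for continuous outcomes, citing diet only as an example, and Aim 3 builds on the same models.
- *That the main conclusions are at risk.* Child diet is described as being of primary interest and is the only outcome with a power calculation.

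**Conclusion.** The point holds as an optional improvement in precision and pre-specification for Aim 1. It is not an error or a contradiction. Under an even 0.25 SD shift, the obesity comparison alone has 30% to 56% power where z-score has 78%. That gap depends on assumed prevalences, a normal z-score, an unadjusted comparison and a shift across all children. It narrows to 56% against 30% to 56% if the upper 75% shift, and disappears or reverses (about 29% against 30% to 56%) if only the upper half do. Confidence in the reading of the text is high. Confidence in the size is moderate, because the documents supply neither a prevalence nor a weight effect.

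**What to change.** In the Aim 1 section of the SAP:
- Add multiple linear regression of baseline BMI z-score on exposure group as a pre-specified supporting analysis.
- Keep logistic regression on obesity as the lead weight analysis, and state the percentile cut-off that defines obesity.
- Use the listed covariates for both weight models, but leave the child's reported fruit and vegetable intake out of the main adjustment set. The programme is meant to raise that intake, so adjusting for it would remove part of any effect on weight.
- Commit to reporting both weight results whichever way they point. Label z-score as supporting, not to be used to claim an effect on its own.

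No change is needed for Aims 2 and 3.

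The cost is a few sentences and a few extra model fits, with no new data. The drawback is one more weight result, which may disagree with the obesity result and is harder to communicate than a prevalence.
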